**Purpose of Study**

- The incidence of urinary tract infection (UTI) in women undergoing pelvic floor gynecologic surgery is high, ranging from 10-64% (Falagas, Athanasiou, Iavazzo, Tokas, & Antsaklis, 2008). A recent randomized trial showed that cranberry juice capsules significantly reduced the incidence of UTI in patients undergoing elective gynecologic surgery (19% vs 38%; odds ratio 0.38 with confidence interval 0.19-0.79) (Foxman, Cronenwett, Spino, Berger, & Morgan, 2015).
- Cincinnati Urogynecology Associates, TriHealth Inc incorporated this clinical regimen into their standard practice in early 2016. Currently, all patients who undergo pelvic floor gynecologic surgery and are discharged from the hospital with an indwelling urinary catheter postoperatively are prescribed cranberry juice capsules to reduce the risk of UTI.
- The purpose of this study is to determine if the addition of cranberry juice capsules to our discharge medication regimen for patients discharged home with an indwelling urinary catheter following pelvic floor gynecology surgery reduced the incidence of UTI.
  - **Primary Aim:** To determine the incidence of UTI in patients who were discharged home with an indwelling urinary catheter following pelvic floor gynecologic surgery in those who were prescribed cranberry juice capsules compared to those who were not.
  - **Secondary Aim:** To determine potential risk factors for postoperative UTI, other than urinary catheter use, such as certain demographic and perioperative factors including the following:
    - Age, race, BMI, tobacco use, medical comorbidities, type of surgery performed, type of anesthesia, intraoperative intravenous fluid administration, estimated blood loss, and duration of catheter use.

### Hypothesis or Research Question

- We hypothesize that the addition of cranberry juice capsules reduced the incidence of UTI in patients discharged home with an indwelling urinary catheter following pelvic floor gynecologic surgery, compared to patients that had similar treatment without cranberry capsules.
- We further hypothesize that the addition of cranberry juice capsules reduced the duration of catheter use for those patients requiring postoperative catheterization following pelvic floor gynecologic surgery.

### Background

Urinary tract infections (UTI) continue to be one of the most common healthcare-associated infections encountered today (Magill et al., 2012). The majority of these healthcare-associated UTIs are attributed to the use of urinary catheters (Hooton et al., 2010). Unfortunately, urinary catheter use is often unavoidable—as in the setting of postoperative urinary retention (POUR). Generally speaking, POUR can be characterized by any impairment in bladder emptying following surgery (Geller, 2014). Previous research has illustrated that POUR is a particularly common issue following urogynecologic surgery, with incidence rates of 1.4-43% (Dorflinger & Monga, 2001; Hakvoort, Elberink, Vollebregt, Ploeg, & Emanuel, 2004; Partoll, 2002). This means that a substantial number of patients will be discharged from the hospital with urinary catheters, putting them at substantially increased risk of developing a postoperative UTI. From an internal review of previously completed studies, approximately 54% and 25% of patients are discharged with a catheter following pelvic reconstructive surgery and suburethral sling procedures, respectively (Crisp et al., 2016).

The incidence of UTI has been estimated to be 3-4% per year for women in the general population (Foxman, 2014). However, for women undergoing urogynecologic surgery, the incidence of UTI is significantly greater, ranging from 10-64% (Falagas et al., 2008). As alluded to above, this increased incidence is likely related to postoperative urinary catheter use. Other risk factors for postoperative UTI have been postulated including age, menopausal status, history of recurrent UTIs, duration of catheter use, and increased distance between the urethra and anus (Foxman et al., 2015; Sutkin et al., 2010).

Previously, there has been much focus on the use of antibiotics to reduce the incidence of UTI in patients with indwelling urinary catheters. According to the most recent Cochrane Review, there remains limited evidence to indicate that receiving prophylactic antibiotics reduces the rate of bacteriuria and other signs of infection in surgical patients who undergo bladder drainage for greater than 24 hours postoperatively (Lusardi, Lipp, & Shaw, 2013). More recently, the focus of UTI prevention has turned to cranberry capsules.

Cranberry products are a potential nonantimicrobial method for UTI prevention, as cranberry proanthocyanidins have been shown to inhibit the adherence of P-fimbriated *Escherichia coli* to uroepithelial cells (Howell, Vorsa, Der Marderosian, & Foo, 1998). Because *E coli* is the culprit behind most UTIs, cranberry products remain an appealing UTI prevention strategy. However,

the evidence continues to be conflicting (Jepson, Williams, & Craig, 2012; Juthani-Mehta et al., 2016).

A recent randomized trial published in a high-impact journal showed that cranberry juice capsules significantly reduced the incidence of UTI in patients undergoing elective gynecologic surgery (19% vs 38%; odds ratio 0.38 with confidence interval 0.19-0.79) (Foxman et al., 2015). As a result of this new data, Cincinnati Urogynecology Associates, TriHealth Inc incorporated cranberry capsules into their standard practice as of March 2016. This change was made in an effort to reduce the incidence of UTI in patients requiring urinary catheterization following urogynecologic surgery. Currently, all patients who undergo urogynecologic surgery and are discharged from the hospital with an indwelling urinary catheter postoperatively are prescribed cranberry juice capsules, in addition to the standard discharge medication regimen.

However, the use of cranberry capsules has not been consistently shown to improve these outcomes in other subgroups of patients at risk (Juthani-Mehta et al., 2016). Furthermore, compliance and actual use of the capsules is uncertain, since patients may elect not to fill the prescription or fail to take the medication appropriately.

We aim to determine if the addition of cranberry juice capsules to the discharge medication regimen for patients discharged home with an indwelling urinary catheter following pelvic floor gynecology surgery significantly reduced the incidence of UTI, compared to a separate cohort that did not have cranberry prescribed. Given recent publications, our hypothesis is that the addition of cranberry juice capsules did reduce the risk of UTI. If we determine that cranberry capsules did in fact reduce the incidence of UTI in our study population, we can feel confident in continuing to incorporate this prevention method in our standard practice.

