  - Given the fact that Cincinnati Urogynecology Associates, TriHealth Inc typically performs 400 surgeries annually, we estimate that reviewing a total of 12 months of data will result in accessing approximately 400 charts.

● **Data Collection**

- Independent variables: cranberry juice capsules prescribed as part of discharge medication regimen
- Dependent variables: UTI as defined by documentation of positive urine culture or treatment by an involved provider, with documentation in the Epic chart within 6 weeks postoperative.
- Each chart will be reviewed and the following data will be collected or extrapolated:
  - General demographic data – Name, date of birth, age, race, weight, height, BMI, parity, tobacco use, medical comorbidities, date of surgery, surgery performed, date of discharge, intraoperative and postoperative

complications, type of anesthesia, intraoperative intravenous fluid administration, estimated blood loss, discharge medications, postoperative urine cultures, prescribed UTI treatment, duration of catheter use, and any postoperative complications or readmissions (fever, ileus, hematoma, transfusion)

- **Intervention or experimental aspect of the study**
  - No intervention will occur as part of this study.
  - There are no potential risks to the study population by any aspect of the study.
- **Statistical Analysis**
  - The primary outcome is the incidence of UTI in patients who were discharged home with an indwelling urinary catheter after pelvic floor gynecologic surgery. To compare the primary outcome between two groups with/without cranberry capsules, the odds ratio and corresponding confidence interval will be utilized. Descriptive statistics will be generated for demographic information such as age, race, BMI, Parity etc. The independent samples t-tests or Mann-Whitney U test will be employed for continuous variables and the Fisher's exact or Pearson Chi-square tests for categorical variables to test any significant difference between two groups. Logistic regression will be implemented to determine potential risk factors for postoperative UTI.

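### The primary cranberry odds ratio compares two calendar-year cohorts with no stated adjustment, and recurrent-UTI history, a risk factor the protocol itself names, has no defined data field

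*Combined protocol and SAP*

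**What the plan says.** All references are to the combined protocol and SAP.

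- **Background** lists postulated risk factors: "Other risk factors for postoperative UTI have been postulated including age, menopausal status, history of recurrent UTIs, duration of catheter use". A fifth, urethra-to-anus distance, follows.
- **Purpose of Study, Secondary Aim** itemises ten factors, beginning "Age, race, BMI, tobacco use, medical comorbidities, type of surgery performed, type of anesthesia" and ending with duration of catheter use. Recurrent-UTI history is not among them.
- **Research Plan, Data Collection** opens with "Each chart will be reviewed and the following data will be collected or extrapolated". The baseline part of the list includes "age, race, weight, height, BMI, parity, tobacco use, medical comorbidities, date of surgery, surgery performed, date of discharge". The UTI items are "postoperative urine cultures, prescribed UTI treatment, duration of catheter use, and any postoperative complications or readmissions", which describe the outcome and not the patient's history.
- **Research Plan, Statistical Analysis**: for the primary outcome, "the odds ratio and corresponding confidence interval will be utilized", with no covariate named. Group comparisons of the collected variables are planned "to test any significant difference between two groups". The regression has a separate purpose: "Logistic regression will be implemented to determine potential risk factors for postoperative UTI". No covariate list is given, and nothing says that it will yield an adjusted cranberry effect.
- **Research Plan, Sample size** defines exposure by year: 2016 exposed, 2015 unexposed.

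**The concern.** Exposure is set by calendar period and not by randomisation, so the crude odds ratio measures the cranberry effect only if the two cohorts had similar baseline risk. The planned between-group tests are the reader's one check on that, and they can cover only what was abstracted. A patient's earlier UTI history is an obvious item to look at, and the protocol names it. As written, it may be recorded for some patients, in one year more than the other, or not at all.

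Two things are at stake. The secondary aim may report on risk factors without one that the protocol itself cites. And a reader of the primary result could not see whether the odds ratio holds after adjusting for even the basic factors already collected. The Background says that a favourable result would give the practice confidence to continue the regimen, so that question will be asked.

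**Working it through.** **The plan's own figures.** 400 surgeries a year × 12/12 months = 400 charts, as stated. The cited randomised trial: (0.19/0.81) / (0.38/0.62) = 0.383, matching the stated 0.38.

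**Analysable patients and events.** The Background gives 25% (sling) and 54% (reconstructive) discharged with a catheter; a mixed caseload lies between.
- Patients: 0.25 × 400 = 100 to 0.54 × 400 = 216, so 50 to 108 per year, before exclusions.
- Average risk at the cited rates with equal groups: (19% + 38%)/2 = 28.5%.
- Events: 100 × 0.285 = 28.5 to 216 × 0.285 = 61.6. If 20% are excluded (assumption): 22.8 to 49.2.

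**Size of a systematic imbalance.** The documents give no prevalence or odds ratio for recurrent-UTI history, so these inputs are assumptions: history odds ratio 2 or 3, UTI risk without it 20% or 30%, no cranberry effect. Risk in a year = p × r1 + (1 − p) × r0, where p is the prevalence of history, r0 the risk without it and r1 the risk with it. For r0 = 20%, r1 = 33.3% or 42.9%; for r0 = 30%, r1 = 46.2% or 56.3%.

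| History 2015 vs 2016 | r0 | History OR | UTI risk 2015 vs 2016 | Crude cranberry OR |
|---|---|---|---|---|
| equal | any | any | equal | 1.00 |
| 37.5% vs 27.5% | 20% | 2 | 25.0% vs 23.7% | 0.93 |
| 37.5% vs 27.5% | 20% | 3 | 28.6% vs 26.3% | 0.89 |
| 25% vs 15% | 30% | 2 | 34.0% vs 32.4% | 0.93 |
| 25% vs 15% | 30% | 3 | 36.6% vs 33.9% | 0.89 |
| 50% vs 30% | 20% | 2 | 26.7% vs 24.0% | 0.87 |
| 50% vs 30% | 20% | 3 | 31.4% vs 26.9% | 0.80 |
| 30% vs 10% | 30% | 2 | 34.8% vs 31.6% | 0.86 |
| 30% vs 10% | 30% | 3 | 37.9% vs 32.6% | 0.79 |

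With the years reversed the values are the reciprocals: 1.08-1.12 for 10 points and 1.15-1.26 for 20 points.

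**Against sampling error.** With no effect and 25% risk, the standard error of the log odds ratio is √(2 / (n × 0.25 × 0.75)) = 0.462 for n = 50 and 0.314 for n = 108 per year. The null 95% range, exp(±1.96 × SE), is 0.40-2.47 and 0.54-1.85. Every shift in the table lies well inside both.

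**Room for adjustment (events per parameter).**

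| Model | 28.5 to 61.6 events | 22.8 to 49.2 events |
|---|---|---|
| cranberry + age + history (3) | 9.5 to 20.5 | 7.6 to 16.4 |
| plus two-level surgery type (4) | 7.1 to 15.4 | 5.7 to 12.3 |
| plus a not-documented category for history (5) | 5.7 to 12.3 | 4.6 to 9.8 |
| ten listed factors + history + cranberry (12) | 2.4 to 5.1 | 1.9 to 4.1 |

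The last row counts one parameter per factor. That is optimistic, because race, surgery type, anesthesia and comorbidities may each need more.

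**The case against.** The strongest reply is that no confounding mechanism is shown. Cranberry was introduced as a policy for all patients discharged with a catheter, not chosen according to UTI history. The Research Plan holds constant the practice and the indications and uses similar months. This stands: a reader might infer that the 2015 and 2016 cohorts differ or that the crude result is biased, but no text says so and no direction can be given.

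A reader might also infer that recurrent-UTI history will not be collected. That goes too far. The secondary-aim list is worded as open-ended, and the medical comorbidities item could include it. What the documents support is narrower: the item is undefined, so nothing ensures that the history is abstracted, or in the same way for both years.

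Nor should chance imbalance be counted as bias. At an assumed 20% prevalence, the SD of the between-year difference is √(2 × 0.2 × 0.8 / n) = 0.080 (n = 50) or 0.054 (n = 108). A gap of at least 10 points then arises by chance with probability 21% or 7%; at 32.5% prevalence the figures are 29% and 12%. That variation is already in the crude interval. Only a systematic shift would add to it.

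Finally, menopausal status is also named in the Background and not itemised. It is tempting to give it equal weight, but age partly covers it, the documents give no effect size, and no consequence for the primary comparison can be shown.

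**Conclusion.** The point holds as a low-priority improvement. The primary odds ratio has no stated adjustment in a non-randomised comparison, although age and type of surgery will be in hand, and one risk factor that the protocol cites lacks a defined field. Any systematic bias is of unknown direction and probably modest: about 7-11% on the odds ratio for a 10-point excess of history in 2015 and 13-21% for a 20-point excess, on the assumed risks above. Neither would explain an effect as large as the cited 0.38. The documents do not support a claim that the primary result is confounded or the study invalid. Confidence is medium, because the prevalence and strength of recurrent-UTI history in this population are not given.

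**What to change.** Before abstraction starts:

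1. Define pre-operative history of recurrent UTI as its own field, or as a named component of medical comorbidities, coded yes / no / not documented by the same rule in both years.
2. Tabulate it by year with the other baseline factors, showing the not-documented counts, and list it among the candidate risk factors.
3. Keep the crude odds ratio. Prespecify beside it one cranberry odds ratio adjusted for age and recurrent-UTI history. Add type of surgery as a single two-level term only if the event count allows, and state in advance that rule and the handling of not-documented history.
4. Do not adjust that odds ratio for duration of catheter use, because the Hypothesis section proposes that cranberry affects it.
5. Optionally, record menopausal status for the exploratory risk-factor aim only. Do not put all candidate factors into one model; report them singly and prespecify which few enter a multivariable model.

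**Cost.** One more field in at most about 100-216 charts already due for full review, with history possibly incomplete, and a somewhat wider interval. In simulation, adjusting for history, age and a two-level surgery type raised the standard error of the log odds ratio by about 4-6% with 50 per year and 2-4% with 108. Those runs included no undocumented history, so they are a favourable case. If a not-documented category and a surgery term are both needed, the worst case falls to 4.6 events per parameter, which is why the three-parameter model should be the default.

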## Research Plan

- **Study Design**
  - Retrospective chart review
- **Setting for the study**
  - The retrospective chart review will be performed on TriHealth EPIC platform at one of the various clinical locations.
- **Participants**
  - Study population: All women 18 years of age or older, who underwent pelvic floor gynecologic surgery (for the indication of pelvic organ prolapse or stress urinary incontinence) performed by a physician at Cincinnati Urogynecology Associates, TriHealth Inc between April 2015 and September 2015, and April 2016 and September 2016, who required indwelling urinary catheter use upon discharge from the hospital.
  - A chart review will be performed on all patients who underwent pelvic floor gynecologic surgery performed by a physician at Cincinnati Urogynecology

Associates, TriHealth Inc between April 2015 and September 2015, and April 2016 and September 2016 to determine which patients required discharge with an indwelling urinary catheter.

- The charts of those patients who required catheterization postoperatively will be reviewed further and will make up our study population of interest.
- Inclusion criteria
  - Adults 18 years of age or older
  - Underwent pelvic floor gynecologic surgery (for the indication of pelvic organ prolapse or stress urinary incontinence) performed by a physician at Cincinnati Urogynecology Associates, TriHealth Inc between April 2015 and September 2015, and April 2016 and September 2016
  - Required indwelling urinary catheterization upon discharge from the hospital postoperatively
- Exclusion criteria
  - Intraoperative bladder injury, fistula repair, urethral diverticulectomy, or any other need for prolonged catheterization
  - Complications in the 2 weeks following surgery requiring reoperation and subsequent catheter use
  - Allergy to cranberry or its components
  - Failure to present for both the two-week and six-week postoperative office visit
- Sample size
  - Cranberry juice capsules were incorporated into the standard practice of Cincinnati Urogynecology Associates, TriHealth Inc in mid-March 2016. We plan to review six months of data from similar time frames of 2015 and 2016. This will allow us to capture a similar number of patients in the exposure (cranberry juice capsules, 2016) and no exposure (no cranberry juice capsules, 2015) groups.
  - Given the fact that Cincinnati Urogynecology Associates, TriHealth Inc typically performs 400 surgeries annually, we estimate that reviewing a total of 12 months of data will result in accessing approximately 400 charts.

● **Data Collection**

- Independent variables: cranberry juice capsules prescribed as part of discharge medication regimen
- Dependent variables: UTI as defined by documentation of positive urine culture or treatment by an involved provider, with documentation in the Epic chart within 6 weeks postoperative.
- Each chart will be reviewed and the following data will be collected or extrapolated:
  - General demographic data – Name, date of birth, age, race, weight, height, BMI, parity, tobacco use, medical comorbidities, date of surgery, surgery performed, date of discharge, intraoperative and postoperative

complications, type of anesthesia, intraoperative intravenous fluid administration, estimated blood loss, discharge medications, postoperative urine cultures, prescribed UTI treatment, duration of catheter use, and any postoperative complications or readmissions (fever, ileus, hematoma, transfusion)

- **Intervention or experimental aspect of the study**
  - No intervention will occur as part of this study.
  - There are no potential risks to the study population by any aspect of the study.
- **Statistical Analysis**
  - The primary outcome is the incidence of UTI in patients who were discharged home with an indwelling urinary catheter after pelvic floor gynecologic surgery. To compare the primary outcome between two groups with/without cranberry capsules, the odds ratio and corresponding confidence interval will be utilized. Descriptive statistics will be generated for demographic information such as age, race, BMI, Parity etc. The independent samples t-tests or Mann-Whitney U test will be employed for continuous variables and the Fisher's exact or Pearson Chi-square tests for categorical variables to test any significant difference between two groups. Logistic regression will be implemented to determine potential risk factors for postoperative UTI.

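### Does labelling the two groups by year under Sample size leave it unclear whether discharge prescription or calendar window defines exposure?

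*Combined protocol and SAP*

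**What the plan says.** Four places in the Combined protocol and SAP describe the exposure in terms of prescribing or of the capsules themselves:

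- The Primary Aim, under Purpose of Study, compares incidence "in those who were prescribed cranberry juice capsules compared to those who were not".
- Data Collection, in the Research Plan, lists "Independent variables: cranberry juice capsules prescribed as part of discharge medication regimen".
- The Background describes the comparison as "compared to a separate cohort that did not have cranberry prescribed".
- Statistical Analysis states: "To compare the primary outcome between two groups with/without cranberry capsules, the odds ratio and corresponding confidence interval will be utilized".

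A fifth place adds calendar years. The Sample size item explains that similar six-month periods of 2015 and 2016 should give similar numbers in the "exposure (cranberry juice capsules, 2016) and no exposure (no cranberry juice capsules, 2015) groups".

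The plan also says why year and prescription should agree. Sample size dates the change in practice to mid-March 2016, and the second window opens in April 2016. The Background states: "Currently, all patients who undergo urogynecologic surgery and are discharged from the hospital with an indwelling urinary catheter postoperatively are prescribed cranberry juice capsules". The exclusion criteria include "Allergy to cranberry or its components". Among the items taken from every chart are "discharge medications, postoperative urine cultures, prescribed UTI treatment, duration of catheter use", and date of surgery is on the same list.

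**The concern.** Two rules for forming the groups appear, and no sentence ranks them. Statistical Analysis, where the primary odds ratio is specified, uses wording that fits either. A woman operated on in 2016 without a cranberry prescription would be unexposed by prescription and exposed by year, and the reverse holds for a 2015 woman who had one. Apart from cranberry allergy, no exclusion is aimed at such women.

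The two rules also answer different questions. Grouping by year compares two periods of practice, and it dilutes a true effect if some 2016 women went without capsules. Grouping by prescription compares individual exposure, but it allows selection within a year if the unprescribed women differ in risk. Exposure and outcome come from the same chart, so a choice left open could in principle be made with UTI results in view.

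**Working it through.** **Reading the text.** Prescribed or not prescribed is a complete split. Under the variable list, a 2016 chart with no capsules among the discharge medications is unexposed, and a 2015 chart with them is exposed. The year labels stand in a parenthesis about accrual, assign no individual woman, and name the capsules beside each year. They read as a description of where the two groups are expected to come from.

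**Group sizes.** The plan gives 400 surgeries a year, and two six-month windows make 12 months: 400 × 12/12 = 400 charts, which reproduces its figure. One window holds 400 × 6/12 = 200 surgeries. The Background puts discharge with a catheter at 54% after reconstructive surgery and 25% after sling procedures, so 200 × 0.54 = 108 or 200 × 0.25 = 50 women per window, before exclusions.

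**Effect on the plan's own account.** With no discordant chart the two groupings contain the same women and give the same odds ratio. The difference is zero.

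**Bound if discordant charts existed.** Assume about 30% UTI in each window, so the odds ratio by window is 1.00. Move k unprescribed 2016 women to the unexposed group. With x events among N per window:

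- all k had a UTI: (x−k)/(N−k) against (x+k)/(N+k)
- none had a UTI: x/(N−k) against x/(N+k)

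| N, x | k | All with UTI | None with UTI |
|---|---|---|---|
| 108, 32 | 1 | 31/107 vs 33/109, OR 0.94 | 32/107 vs 32/109, OR 1.03 |
| 108, 32 | 5 | 27/103 vs 37/113, OR 0.73 | 32/103 vs 32/113, OR 1.14 |
| 50, 15 | 1 | 14/49 vs 16/51, OR 0.88 | 15/49 vs 15/51, OR 1.06 |
| 50, 15 | 5 | 10/45 vs 20/55, OR 0.50 | 15/45 vs 15/55, OR 1.33 |

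For scale, the standard error of the log odds ratio at k = 0 is √[2(1/32 + 1/76)] = 0.298 for N = 108 and √[2(1/15 + 1/35)] = 0.436 for N = 50. The 95% intervals around 1.00 are 0.56 to 1.79 and 0.43 to 2.35. Even the five-chart extremes lie inside them.

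**A milder case, N = 108.** Let 5% of 2016 women be unprescribed, with a risk of 45% against 30% overall. The remaining 2016 women have risk (0.30 − 0.05 × 0.45)/0.95 = 0.292. The enlarged unexposed group has (0.30 + 0.05 × 0.45)/1.05 = 0.307. The odds ratio is 0.93. With a risk of 15% in place of 45% it is 1.07. Either shift is about 0.071/0.298 = 0.24 of a standard error.

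**Dilution under grouping by year.** The cited trial's 19% and 38% give (0.19/0.81)/(0.38/0.62) = 0.383, matching its reported 0.38. If a share f of 2016 women are unprescribed and carry the 38% risk, the 2016 risk is 0.19(1−f) + 0.38f. At f = 5% this is 0.1995, giving an odds ratio of 0.407. Power (two-proportion z test, two-sided 0.05 assumed because the plan states no level, N = 108) is then 0.84 by year and 0.88 by prescription, against 0.88 for both at f = 0. At f = 15% it is 0.74 and 0.87. With 50 per window it is 0.56 for both at f = 0, and 0.42 and 0.54 at f = 15%.

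**The case for a change.** The strongest case for a change is that the statement about prescribing to everyone describes practice when the plan was written, with the study to begin in January 2017. It is not a measured rate for April to September 2016, when the practice was new. The Background itself doubts whether patients fill the prescription or take the capsules. A reader who started from Sample size could group by date of surgery. Naming the governing rule would cost one sentence, and a count of discordant charts would need no new data.

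Part of this stands. There is no explicit tie-break, no planned count of discordant charts, and no measured prescribing rate. But the statement follows directly on the Background's report that capsules became standard as of March 2016, so it reads most naturally as covering the second window. Doubt about filling or taking capsules concerns adherence, and it affects neither grouping, since both disregard actual use. The suggested sentence would repeat what the variable list already says. A cross-tabulation of prescription by window is a routine data check that an analyst would make from fields already collected.

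**Conclusion.** No change is called for. The plan defines exposure by discharge prescription in its aim, its Background and its variable list, and that definition classifies every chart. The years under Sample size are descriptive labels for groups the plan expects to match it. On the plan's own account the effect on the primary odds ratio is zero, and the documents contain no evidence of a discordant woman. Every non-zero figure above rests on assumed discordance; the bounds and the milder case also assume a 30% risk, and the power figures assume the cited trial's rates and a two-sided 0.05 level. The wider bounds further require that all, or none, of the moved women had a UTI. If discordant charts did turn up, the written definition would still place them. Neither grouping removes other differences between 2015 and 2016, so choosing between them would not strengthen the design on that score.

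### UTI is scored on a positive culture or treatment alone and analysed only as that composite, so a change in culturing or prescribing between 2015 and 2016 could not be told from a cranberry effect

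*Combined protocol and SAP*

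**What the plan says.** Under Data Collection, the Research Plan gives the dependent variable as "UTI as defined by documentation of positive urine culture or treatment by an involved provider", "with documentation in the Epic chart within 6 weeks postoperative". The conjunction is an either/or. No symptom criterion, colony-count threshold, culture confirmation of treated cases or masked outcome review is described.

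The data list in the same section abstracts the two components as separate items: "postoperative urine cultures, prescribed UTI treatment".

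Under Statistical Analysis, the plan for the main comparison is: "To compare the primary outcome between two groups with/without cranberry capsules", "the odds ratio and corresponding confidence interval will be utilized". The rest of that section covers descriptive statistics, between-group tests and a logistic regression for risk factors. Neither component is analysed separately.

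The Sample size item sets exposure by period: "exposure (cranberry juice capsules, 2016) and no exposure (no cranberry juice capsules, 2015) groups". The Background says that the practice "incorporated cranberry capsules into their standard practice as of March 2016", with the aim of lowering UTI in catheterised patients.

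**The concern.** Every woman in the study went home with an indwelling catheter. A positive culture with no treatment counts as an event, and so does treatment with no culture or with a negative one. Both components depend partly on clinical decisions: whom to culture and whom to treat empirically.

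Two consequences follow. If false-positive events are equally common in both years, the odds ratio is pulled toward 1 and power is lost. If they differ between years, the composite can show an apparent effect where there is none, or hide a real one. Year and exposure coincide in this design, so the single odds ratio cannot separate the two explanations.

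The result has a use. The Background says that a favourable finding would support continuing capsules as standard practice, and the protocol plans publication.

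**Working it through.** **Inputs from the documents**
- Cited randomised trial (Purpose of Study; Background): UTI 19% with capsules, 38% without, odds ratio 0.38.
- About 400 charts over the two six-month windows (Research Plan, Sample size).
- Discharged with a catheter: 54% after reconstructive surgery, 25% after sling procedures (Background).

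**Reproducing the quoted figures**
- Odds ratio: (0.19/0.81)/(0.38/0.62) = 0.383, which agrees with 0.38.
- Charts: 400 surgeries a year × 12/12 = 400.
- Women per group, before exclusions: 400 × 0.25 / 2 = 50 to 400 × 0.54 / 2 = 108. The upper figure applies the reconstructive rate to every chart, so it is the favourable end.

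**Assumptions (not in the documents)**
- f is the share of women without true UTI who nevertheless score as events. Sensitivity is taken as perfect.
- The cited trial's rates stand in for true risks.
- Power uses the two-proportion normal approximation at two-sided alpha 0.05. The plan states no alpha or power.

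Observed risk = p + (1 − p) × f.

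**(a) Same f in both years, true risks 38% and 19%**

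| f | 2015 | 2016 | OR | Power, 108 per group | Power, 50 per group |
|---|---|---|---|---|---|
| 0 | 38.0% | 19.0% | 0.38 | 88% | 56% |
| 5% | 41.1% | 23.1% | 0.43 | 82% | 49% |
| 10% | 44.2% | 27.1% | 0.47 | 75% | 43% |
| 15% | 47.3% | 31.2% | 0.50 | 68% | 38% |

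Example for f = 10%: 0.38 + 0.62 × 0.10 = 0.442; 0.19 + 0.81 × 0.10 = 0.271; OR = (0.271/0.729)/(0.442/0.558) = 0.469.

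**(b) No cranberry effect, true risk assumed 30% in both years, f falling between years**
- From 20% to 10%: 0.30 + 0.70 × 0.20 = 0.44 against 0.30 + 0.70 × 0.10 = 0.37; OR = (0.37/0.63)/(0.44/0.56) = 0.75.
- From 10% to 5%: 0.37 against 0.30 + 0.70 × 0.05 = 0.335; OR = (0.335/0.665)/(0.37/0.63) = 0.86.
- Chance of a significant result favouring cranberry, against a nominal 2.5%: about 18% and 8% at 108 per group; about 11% and 6% at 50 per group.

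**(c) Would requiring both culture and treatment solve it?** Take no effect, true risk 30% in both years, every case treated, no false positives, and culturing of cases falling from 80% to 60% (all assumed). The either/or definition gives 30% against 30%, OR 1.00. The both-required definition gives 0.30 × 0.80 = 24% against 0.30 × 0.60 = 18%; OR = (0.18/0.82)/(0.24/0.76) = 0.70. The stricter endpoint is itself sensitive to culturing habits.

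**The case against.** An either/or definition is a reasonable choice for a chart review, because it catches women who were treated without a culture. A stricter definition has its own price. If requiring both components captured 70% of true cases with no false positives (an assumption), the risks would be 26.6% and 13.3%, with power of 69% at 108 per group and 38% at 50. That is about the same loss as in the 15% row above. This stands: it is a reason to leave the primary definition alone, but not a reason to leave the components unexamined.

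Some stronger readings are tempting, and the documents do not support them.
- *Treatment for any reason counts.* The definition says only treatment, but it is defining UTI, and the abstracted field is worded as UTI treatment. Read together, they largely settle the meaning; what remains is a wording mismatch.
- *Providers treated differently because they knew the regimen.* That they knew it is a fair inference from an openly adopted policy, but it is not stated, and an involved provider need not belong to the practice. Nothing in the documents says that culturing or prescribing changed. The study was to begin in January 2017, after both surgical windows had closed, so the study itself is unlikely to have prompted such a change.
- *A cranberry effect should be claimed only if the both-required analysis agrees.* Calculation (c) shows why that condition would be unsafe.

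Drift between periods is a general limit of before/after designs. That is also true, but here the data needed to look for one form of it are already being abstracted.

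**Conclusion.** The concern holds as a gap in the analysis. The plan collects both components and analyses only their union, in a design where the year determines exposure. It therefore has no check on whether a difference in the composite reflects infection or ascertainment.

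The size cannot be determined from the documents. Under the assumptions above, shared false positives of 5 to 15% cost 6 to 20 percentage points of power at 108 per group and 7 to 18 points at 50. A halving of false positives between years produces an odds ratio of 0.75 to 0.86 with no true effect. These figures show that the problem could matter; they do not estimate what happened, and they do not show that the primary result will be biased. This is an inexpensive improvement to make before abstraction, not a flaw that invalidates the primary comparison.

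**What to change.** 1. Keep the stated primary definition, and word its treatment component to match the abstracted field, "postoperative urine cultures, prescribed UTI treatment".
2. Pre-specify as sensitivity analyses the 2016-against-2015 odds ratio and confidence interval for (a) positive culture, (b) UTI treatment and (c) both.
3. Report the proportion of women with any postoperative urine culture in each year.
4. State in advance that, if the components point in different directions or the proportion cultured differs between years, the composite result will be reported as possibly reflecting changed ascertainment. The word possibly matters, since fewer true infections could also lead to fewer cultures.
5. Do not make agreement of analysis (c) a condition for claiming an effect.

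The cost is a short protocol change and a few table rows from fields already abstracted. Each sensitivity analysis will have no more events than the composite, so intervals will generally be wider, particularly for (c).
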